Plan for reporting events to the Yale IRB that are unexpected AND related AND involve risk of harm to subjects or others:

The PI will report to the IRB any incident, experience or outcome that meets ALL 3 of the following criteria:

- 1) Is unexpected (in terms of nature, specificity, severity, or frequency) given (a) the research procedures described in the protocol-related documents, such as the IRB-approved protocol and informed consent document and (b) the characteristics of the subject population being studied; and
- 2) Is related or possibly related to participation in the research (possibly related means there is a reasonable possibility that the incident, experience, or outcome may have been caused by the procedures involved in the research); and
- 3) Suggests that the research places subjects or others at greater risk of harm (including physical, psychological, economic, legal, or social harm) than was previously known or recognized.

Unanticipated Problems Involving Risks to Subjects or Others (UPIRSOs) may be medical or non-medical in nature, and include – but are not limited to – serious, unexpected, and related adverse events.

All related events involving risk but not meeting the prompt reporting requirements described above will be reported to the IRB in summary form at the time of continuing review. If appropriate, such summary may be a simple brief statement that events have occurred at the expected frequency and level of severity as previously documented.

Plan for reporting adverse events to the PI, Safety Monitor, and study team:

For the current study, the following individuals, funding, and/or regulatory agencies will be notified:

- PI
- All Co-Investigators listed on the protocol; and
- Yale IRB

The PI will review all adverse events upon completion of every study subject. The PI will evaluate the frequency and severity of adverse events and determine if modifications to the protocol or consent form are required.

Procedures for providing follow up care:

Study participant safety will be monitored by the study team and reported to the PI at all clinical and assessment visits and referrals will be provided if warranted and/or requested. If a study participant experiences any psychiatric symptoms or distress (e.g., depressive symptoms or suicidality) at any stage of study participation he/she will receive short-term treatment and support from the study treatment team (which includes psychologists) and will be connected to a local emergency department (e.g., the Crisis Intervention Unit at Yale-New Haven Hospital) and her pediatrician or therapist for ongoing care.

Other Potential Issues Relating to Stopping Rules for the Study Include:

- 1) New Information: It is unlikely that any new information would become available during this trial that would necessitate stopping the trial. If new data become available, these will be evaluated.
- 2) Limits of Assumptions: It is possible that baseline differences between the treatment conditions, excessive attrition, and/or missing data could limit the value of data analysis. Baseline differences across treatment groups, if present, will be evaluated twice yearly and considered in relation to potential effects on the power to detect differences in the primary outcomes. If these effects were to develop and be sizeable, alterations to the randomization schedule would be considered.

Limits of Rules: There are other situations that could occur that might warrant stopping the trial and/or including a section on the safety report entitled “Other situations that have occurred since the last safety report that warrant discussion” to allow for communication of concerns.

13. Statistical Considerations: Describe the statistical analyses that support the study design.

Continuous variables will be examined for normality using probability plots and Kolmogorov-Smirnov tests. If normality is not satisfied and transformations do not achieve acceptable normality, nonparametric strategies will be considered. Analyses will be intent-to-treat. Outcomes will be tested at the $\alpha=0.05$ threshold.

As this is a pilot study, results are anticipated to yield significant impact by providing effect sizes that will allow outcome variables to be selected and sample size to be calculated for a fully-powered randomized controlled trial that includes a control group. Descriptive statistics will characterize putative outcome variables (Aim 1: general health, trauma symptoms, weight/shape concerns) and variability, including confidence intervals. Exploratory analyses will identify potential outcome, predictor, and moderator variables to be tested in an adequately-powered RCT comparing CBT for weight-related bullying with a control group in preventing disordered eating and weight gain.

Variables and Analyses for Primary Aims. (1) **Establish** feasibility: descriptive statistics will quantify total/last sessions attended, and clinician adherence (ratings of recorded sessions). (2) Acceptability: descriptive statistics will quantify treatment ratings (clinician/patient). (3) **Test** initial efficacy at post relative to baseline on clinical outcomes: descriptive statistics (means and variability, including confidence intervals) will characterize change and paired t-tests will test changes from baseline to post in (a) improvements in general health (SF12), (b) reductions in traumatic symptoms (CRIES) and (c) reductions in weight/shape concerns (EDEQ). Repeated-measures growth mixture models (103) will explore response over time for these three variables (SF12, CRIES, EDEQ). This approach allows for different numbers of observations per participant, uses all available data on each participant, accounts for clustered data observations (e.g., parent-child), and is unaffected by data missing at random. Because we cannot *a priori* predict the shape of the response over time, we will first treat time as categorical and then test for polynomial trends. Attendance will be examined for informative dropout patterns.

Variables and Analyses for Secondary Aims: **Explore** whether clinical features improve with treatment: descriptive statistics (means and variability, including confidence intervals) will characterize change and paired t-tests will test changes from baseline to post in (1) eating disorder behaviors (episode frequency), (2) depression (PHQ), (3) weight (BMI-z). As with primary aims, repeated-measures growth mixture models will explore response over time for these variables.

Power Analysis and Justification of Sample Size for Pilot Study. Power estimates for the pilot RCT were based on change in weight concerns during CBT-ED for adolescents (104). Assuming a two-sided test at $\alpha=0.05$ threshold, we have 80% power to detect clinically-meaningful within-subject effects ($d=0.64$) with a sample size of 23. With a sample size of 30, we have 80% power to detect clinically-meaningful effects if there is 20% dropout. Thus, we have a reasonable chance of finding statistically significant change, even in this pilot study.

SECTION II: RESEARCH INVOLVING DRUGS, BIOLOGICS, RADIOTRACERS, PLACEBOS AND DEVICES

If this section (or one of its parts, A or B) is not applicable, check off N/A and delete the rest of the section.

A. RADIOTRACERS N/A

B. DRUGS/BIOLOGICS N/A

B. DEVICES N/A

SECTION III: RECRUITMENT/CONSENT AND ASSENT PROCEDURES

1. Targeted Enrollment: Give the number of subjects:

- Targeted for enrollment at Yale for this protocol: **30**
- If this is a multi-site study, give the total number of subjects targeted across all sites: n/a

2. Indicate recruitment methods below. Attach copies of any recruitment materials that will be used.

 Flyers	 Internet/web postings	 Radio
 Posters	 Mass email solicitation	 Telephone
 Letter	 Departmental/Center website	 Television
 Medical record review*	 Departmental/Center research boards	 Newspaper
 Departmental/Center newsletters	 Web-based clinical trial registries	 Clinicaltrials.gov
 YCCI Recruitment database	 Social Media (Twitter/Facebook):	

 Other: EPIC direct-to-patient	
 Other: messages to provider EPIC inbox	

* Requests for medical records should be made through JDAT as described at
<http://medicine.yale.edu/ycci/oncore/availableservices/datarequests/datarequests.aspx>

3. Recruitment Procedures:

- Describe how potential subjects will be identified.

Participants will be recruited using widespread media advertising, internet and printed materials throughout the community. The study will also be posted on the website for clinical trials at Yale and on websites run by the Yale Program for Obesity, Weight, and Eating Research (including Yale Teen POWER).

b. Describe how potential subjects are contacted.

Pre-screening. Interested parents/adolescents will be screened briefly to determine whether the teen is likely to be eligible to participate in the study. If they seem potentially eligible and interested in the study, parents and their children will be scheduled for an initial assessment visit.

Initial Assessment. After initial contact, study clinicians will meet with potential participants to discuss the study, the treatments, the assessments, and the informed consent procedures and forms.

EPIC Direct to Patient MyChart confidential messaging will be utilized for recruitment of subjects meeting specific parameters (youth meeting age and gender criteria, using other exclusion criteria to refine sample to those likely eligible). The following template will be utilized:

Title of study, Phase or type of study: Cognitive-Behavioral Therapy for Teens Who Experienced Weight-related Bullying

Principal Investigator: [name].

Study Contact: [name]. [contact]

Description:

Teens 11 to 17 years old who have experienced weight-based bullying (being teased or bullied because of weight) may be eligible to participate in a free and confidential treatment study that may help with coping. Talk therapy is provided (no medications). Participants will receive up to \$80 compensation. To learn more or see if you are eligible to participate, please call the Yale Program for Obesity, Weight, and Eating Research at: [contact] or visit <http://power.yale.edu>

Please indicate how often you would like to receive new names of potential participants daily weekly

EPIC Inbox Messages will be utilized to send information to providers about referring subjects to the treatment study. Providers will receive the inbox message if they meet specific parameters (seeing patients under age 18). The following template will be utilized:

Title of study, Phase or type of study: Cognitive-Behavioral Therapy for Teens Who Experienced Weight-related Bullying

Principal Investigator: [name].

Study Contact: [name]. [contact]

Description:

We are recruiting adolescents who have experienced weight-based bullying for a trauma-focused treatment. Bullying is a risk factor for future eating disorders and weight gain.

About the treatment:

- The study treats distress related to weight-based bullying by improving coping
- There is no cost to the patient, and no cost to their insurance
- All teens receive a behavioral trauma treatment
- Treatment lasts 3

Who to refer:

- Adolescents between 11-17 years old
- Teens who report being bullied (we will assess bullying and emotional distress)

To refer a patient who may be eligible:

- The **teen or parent** can call: [contact] or email: [contact]
- The **teen or parent** can request information: <http://m.yale.edu/teenpower>
- **Direct-to-provider:** email [name] at [contact]

c. Who is recruiting potential subjects?

PI and study staff will be recruiting potential participants.

4. Assessment of Current Health Provider Relationship for HIPAA Consideration: Does the Investigator or any member of the research team have a direct existing clinical relationship with any potential subject?

Yes, all subjects

Yes, some of the subjects

No

If yes, describe the nature of this relationship.

5. Request for waiver of HIPAA authorization: (When requesting a waiver of HIPAA Authorization for either the entire study, or for recruitment purposes only. Note: if you are collecting PHI as part of a phone or email screen, you must request a HIPAA waiver for recruitment purposes.)

Choose one:

For entire study

For recruitment/screening purposes only

For inclusion of non-English speaking subject if short form is being used and there is no translated HIPAA research authorization form available on the University's HIPAA website at hipaa.yale.edu.

- Describe why it would be impracticable to obtain the subject's authorization for use/disclosure of this data:
- If requesting a waiver of **signed** authorization, describe why it would be impracticable to obtain the subject's signed authorization for use/disclosure of this data:

Potential participants will initially call us in response to advertisements, at which time, if they seem eligible, we will schedule them for an initial assessment and collect contact information. If potential participants elect

to participate, they would then provide informed consent including HIPAA authorization as described at their initial appointment.

The investigator assures that the protected health information for which a Waiver of Authorization has been requested will not be reused or disclosed to any person or entity other than those listed in this application, except as required by law, for authorized oversight of this research study, or as specifically approved for use in another study by an IRB.

Researchers are reminded that unauthorized disclosures of PHI to individuals outside of the Yale HIPAA-Covered entity must be accounted for in the “accounting for disclosures log”, by subject name, purpose, date, recipients, and a description of information provided. Logs are to be forwarded to the Deputy HIPAA Privacy Officer.

6. Process of Consent/Accent: Describe the setting and conditions under which consent/assent will be obtained, including parental permission or surrogate permission and the steps taken to ensure subjects' independent decision-making.

After initial screening and preliminary determination of eligibility, study clinicians will meet with potential participants for an initial intake appointment. At the intake, study clinicians will discuss the study and all procedures, treatments, and risks and obtain written informed consent from one parent and assent from the adolescent. All prospective participants will be free to decide whether or not to participate and enrolled participants are free to withdraw from the study at any time. Alternative treatments will be discussed and referrals offered if requested. Written informed consent from parents, and assent from adolescents, will be obtained after they have the opportunity to discuss and address all questions with a study clinician and/or the PI. If a child turns 18 while in the study, we will have them sign an adult consent form. As talk therapy is minimal risk, and the treatment condition is likely to provide some direct benefit to the adolescent, only one parent signature will be obtained. As this is a telehealth treatment, electronic signatures will be collected.

7. Evaluation of Subject(s) Capacity to Provide Informed Consent/Accent: Indicate how the personnel obtaining consent will assess the potential subject's ability and capacity to consent to the research being proposed.

With all participants, we will describe the study verbally during the consent process and allow participants to ask any questions they might have. To ensure understanding, we will use open-ended questions with all participants to ask that they paraphrase the nature of the research and what they are being asked to do as part of the study, and also summarize the potential risks and benefits of the study.

8. Non-English Speaking Subjects: Explain provisions in place to ensure comprehension for research involving non-English speaking subjects. If enrollment of these subjects is anticipated, translated copies of all consent materials must be submitted for approval prior to use.

n/a

As a limited alternative to the above requirement, will you use the short form* for consenting process if you unexpectedly encounter a non-English speaking individual interested in study participation and the translation of the long form is not possible prior to intended enrollment? YES NO

9. **Consent Waiver:** In certain circumstances, the HIC may grant a waiver of signed consent, or a full waiver of consent, depending on the study. If you will request either a waiver of consent, or a waiver of signed consent for this study, complete the appropriate section below.

Not Requesting any consent waivers

Requesting a waiver of signed consent:

- Recruitment/Screening only** (if for recruitment, the questions in the box below will apply to recruitment activities only)
- Entire Study** (Note that an information sheet may be required.)

For a waiver of signed consent, address the following:

- Would the signed consent form be the only record linking the subject and the research? YES NO
- Does a breach of confidentiality constitute the principal risk to subjects? YES NO

OR

- Does the research pose greater than minimal risk? YES NO
- Does the research include any activities that would require signed consent in a non-research context? YES NO

Requesting a waiver of consent:

- Recruitment/Screening only** (if for recruitment, the questions in the box below will apply to recruitment activities only)
- Entire Study**

SECTION IV: PROTECTION OF RESEARCH SUBJECTS

Confidentiality & Security of Data:

1. What protected health information (medical information along with the HIPAA identifiers) about subjects will be collected and used for the research?

Height, weight, medical and psychosocial history will be collected and used for research.

HIPAA identifiers to be collected:

- Names
- All geographic subdivisions smaller than a State, including: street address, city, county, precinct, zip codes and their equivalent geocodes, except for the initial three digits of a zip code if, according to the current publicly-available data from the Bureau of the Census: (1) the geographic unit formed by combining all zip codes with the same three initial digits contains more than 20,000 people, and (2) the initial three digits of a zip code for all such geographic units containing 20,000 or fewer people is changed to 000.
- Telephone numbers
- E-mail addresses
- All elements of dates for dates related to an individual, including: birth date

2. How will the research data be collected, recorded and stored?

Data will be collected via interview by trained clinicians and data will be collected via surveys using Qualtrics. Data will be recorded using the Zoom application for telehealth (or other platforms approved by Yale School of Medicine) for those participants who consent to audio and/or video recording. Data will be stored on the secure Yale server and/or in locked file cabinets.

3. How will the digital data be stored?

CD DVD Flash Drive Portable Hard Drive Secured Server Laptop Computer Desktop Computer
 Other

4. What methods and procedures will be used to safeguard the confidentiality and security of the identifiable study data and the storage media indicated above during and after the subject's participation in the study?

To ensure confidentiality, all research records will be kept on Yale secure servers and in locked files in the Department of Psychiatry at Yale School of Medicine. All research personnel will be trained and supervised around confidentiality issues. The training will include formal NIH or Yale IRB modules with testing certification as well as HIPAA guidelines to follow around confidentiality. The PI and all essential research personnel will have access to the data. All essential personnel will be included as research staff on the HIC protocol submitted for approval.

All participants will be assigned a study number. Subsequently, participants will be identified only by that number and an encoded version of their initials (e.g., John Smith [adolescent] = JSMI-A). A list of numbers and the corresponding names will be maintained by the PI and stored on a Yale secure serve and/or in a locked research file. Any information published as a result of the study will be such that it will not permit identification of any participant.

Individually identifiable health information will be protected in accordance with the Health Insurance Portability and Accountability Act of 1996. All information collected will remain confidential except when we are legally required to disclose such information by law. These circumstances include knowledge of abuse of a child or elderly person, threats of harm to self or others, and plans to harm to property. Research records may be audited by a regulatory agency within the federal government. Organizations that have a responsibility for protecting human subjects, including the Yale IRB (Human Investigation Committee), may have access to the research records.

All portable devices must contain encryption software, per University Policy 5100. If there is a technical reason a device cannot be encrypted please submit an exception request to the Information Security, Policy and Compliance Office by clicking on url <http://its.yale.edu/egrc> or email [contact]

5. What will be done with the data when the research is completed? Are there plans to destroy the identifiable data? If yes, describe how, by whom and when identifiers will be destroyed. If no, describe how the data and/or identifiers will be secured.

Data will be stored in locked cabinets for 7 years after the final data are collected. At the end of the study, participants will only be identified by their study code.

6. If appropriate, has a Certificate of Confidentiality been obtained?

Yes

SECTION V: POTENTIAL BENEFITS

Potential Benefits: Identify any benefits that may be reasonably expected to result from the research, either to the subject(s) or to society at large. (Payment of subjects is not considered a benefit in this context of the risk benefit assessment.)

The study may have no direct benefit to the participant. The treatment is known to be helpful to youth with distress associated with other forms of trauma, but we do not know if it will be helpful to adolescents who have experienced weight-related bullying. We anticipate that some of the knowledge from this study will be used to improve treatments for adolescents and to increase our understanding of treatments for weight-related bullying.

SECTION VI: RESEARCH ALTERNATIVES AND ECONOMIC CONSIDERATIONS

1. **Alternatives:** What other alternatives are available to the study subjects outside of the research?

Alternatives include community referrals for weight loss counseling, cognitive behavioral therapy and interpersonal psychotherapy for eating disorders. These treatments do not generally address bullying.

2. **Payments for Participation (Economic Considerations):** Describe any payments that will be made to subjects, the amount and schedule of payments, and the conditions for receiving this compensation.

Parents and children will be paid for completing assessments (Mo.1=\$20/each; Mo.2=\$20/each; Post=\$40/child, \$20/parent).

3. **Costs for Participation (Economic Considerations):** Clearly describe the subject's costs associated with participation in the research, and the interventions or procedures of the study that will be provided at no cost to subjects.

The treatment will be provided at no cost to the participants.

4. **In Case of Injury:** This section is required for any research involving more than minimal risk, and for minimal risk research that presents the potential for physical harm (e.g., research involving blood draws).

This treatment is considered to be minimal risk and does not involve the potential for physical harm. Referrals will be provided if indicated.

IMPORTANT REMINDERS

Will this study have a billable service? Yes No

Are there any procedures involved in this protocol that will be performed at YNHH or one of its affiliated entities?
 Yes No

IMPORTANT REMINDER ABOUT RESEARCH AT YNHH

Please note that if this protocol includes Yale-New Haven Hospital patients, including patients at the HRU, the Principal Investigator and any co-investigators who are physicians or mid-level practitioners (includes PAs, APRNs, psychologists and speech pathologists) who may have direct patient contact with patients on YNHH premises must have medical staff appointment and appropriate clinical privileges at YNHH. If you are uncertain whether the study personnel meet the criteria, please telephone the Physician Services Department at [contact]. **By submitting this protocol as a PI, you attest that you and any co-investigator who may have patient contact has a medical staff appointment and appropriate clinical privileges at YNHH.**

BIBLIOGRAPHY

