Exclusion Criteria: Prospective participants will be excluded if the adolescent:

1. Has a medical or psychiatric condition that would require hospitalization or intensive care (e.g., severe anorexia, neurological disorder, psychotic disorders, suicidality);
2. Has uncontrolled medical condition(s) (e.g., uncontrolled diabetes or hypertension);
3. Is pregnant or breastfeeding;
4. Is taking medication(s) or participating in concurrent treatment(s) that focus on trauma-related stress;
5. Began taking hormonal contraceptives less than 3 months prior;
6. Has a developmental or cognitive disorder (e.g., autism spectrum disorder);
7. Has avoidant/restrictive food intake disorder; or
8. Is participating in another clinical research study.

9. How will eligibility be determined, and by whom? Write here

Participants will be interviewed during an initial intake by a study clinician. The structured Mini International Neuropsychiatric Interview (MINI) will be used to assess psychiatric disorders and psychopathology. The MINI along with the Eating Disorder Examination will also determine whether participants have any co-existing psychiatric conditions that require referrals, hospitalization or more intensive/different treatment. Data from the CRIES will be used to determine whether the adolescent is experiencing distress related to bullying (responding “sometimes” or “often” to items about the trauma), in conjunction with clinical assessment.

Final determination of eligibility will be from the PI. Monitoring will occur at treatment visits and referrals will be provided if warranted. If a study participant experiences any psychiatric symptoms or distress (e.g., depressive symptoms or suicidality) at any stage of study participation he/she will receive short-term treatment and support from the PI and study treatment team (which includes psychologists) and will be connected with a local emergency department (e.g., the Crisis Intervention Unit at Yale-New Haven Hospital) and their pediatrician or a therapist for ongoing care.

10. Risks: Describe the reasonably foreseeable risks, including risks to subject privacy, discomforts, or inconveniences associated with subjects participating in the research.

The primary risks of the behavioral interventions, assessment procedures, and unknown treatment efficacy.

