TF-CBT is an established treatment for trauma-related concerns, and CBT-ED are established treatment for disordered eating. TF-CBT is widely used in youth, and CBT-ED is widely used in research and clinical settings, for both youth and adults. The only foreseeable risks include some discomfort or embarrassment when discussing bullying, eating patterns, weight, or body image concerns.

Previous controlled clinical trials conducted by the PI and study team with similar interventions with adult and adolescent participants have not reported problems. Any troublesome effects would be readily identifiable by the experienced study clinicians during repeated evaluations. Thus, the risks of the CBT intervention are judged to be minimal.

Research assessments are noninvasive and should add no substantial risk. The major disadvantages are the time taken to complete them and potential for a breach of confidentiality. Completion of the assessment interviews and surveys may cause some mild anxiety or embarrassment to some participants. Past experiences of the PI and study team indicate that the measures are acceptable to participants. Careful efforts aimed at maintaining confidentiality will be made (as described below).

There is a chance that participants' mood or eating concerns may fail to improve or may worsen during the study. Participants will be provided with short-term treatment and support from the PI and clinical team (which includes psychologists) and/or the participant will be withdrawn from the study if their clinical condition deteriorates to a significant degree. Any participant who is withdrawn will be provided with appropriate referrals.

11. Minimizing Risks: Describe the manner in which the above-mentioned risks will be minimized.

The study clinicians will be carefully trained and supervised by the PI. All study clinicians and study staff will have IRB and ethics training; because of their educational experience and training (e.g., in psychology), they can reasonably be expected to identify potential problems and to take appropriate action as medically indicated.

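### A teen who deteriorates may be withdrawn from the study, not only from treatment, with no stated plan to obtain Post; the baseline-to-Post change can then shift modestly toward improvement

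*Combined protocol and SAP*

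**What the plan says.** Section I, item 10 (Risks) accepts that a participant's "mood or eating concerns may fail to improve or may worsen during the study". It offers two responses: short-term treatment and support, "and/or the participant will be withdrawn from the study if their clinical condition deteriorates to a significant degree". The only stated sequel is: "Any participant who is withdrawn will be provided with appropriate referrals".

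Item 9 (eligibility) and the follow-up care paragraph of item 12 describe the response to distress without mentioning withdrawal. Item 9 says that a participant with symptoms "at any stage of study participation he/she will receive short-term treatment and support from the PI and study treatment team", with connection to outside care.

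Item 13 (Statistical Considerations) declares the analyses intent-to-treat. For initial efficacy, "paired t-tests will test changes from baseline to post in (a) improvements in general health (SF12"), and likewise in CRIES and EDE-Q. Growth mixture models then explore response over time; the plan says that this approach "is unaffected by data missing at random". It adds: "Attendance will be examined for informative dropout patterns". The purpose of the pilot includes "providing effect sizes that will allow outcome variables to be selected and sample size to be calculated" for a later randomised trial.

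In Table 2, CRIES and EDE-Q are collected at Baseline, Month 1, Month 2 and Post. SF12 is collected at Baseline and Post only.

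**The concern.** The rule ties leaving the study to getting worse. If the teen's Post assessment is then not obtained, the missing value is not a random one: it belongs to someone selected for deterioration in mood or eating, which lies close to what the efficacy outcomes measure. A paired t-test needs both values, so it proceeds without that teen. The intent-to-treat statement supplies neither a commitment to collect Post nor a rule for handling its absence.

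With one arm there is no comparison group in which the same loss might offset this. The baseline-to-Post change is the efficacy result, and it is meant to guide the choice of outcomes and the size of the next trial. What is at stake is a somewhat favourable effect size, not the safety record.

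**Working it through.** **The plan's own figure.** Item 13 states 80% power at d = 0.64, two-sided 5%, with 23 teens. The noncentral t distribution for a paired test gives 79.7% at 21, 81.6% at 22 and 83.5% at 23, so the figure holds with a patient to spare. With 20% dropout, 30 × 0.8 = 24 teens remain, giving 85.1%. The dropout allowance therefore protects power. It does nothing about which teens are lost.

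**Inputs for the shift.** From the plan: 30 enrolled, paired test, two-sided 5%. Assumed, because the documents do not give them: k teens withdrawn (1 to 3), and a correlation r between the marker of deterioration that prompts withdrawal and the teen's own change on the outcome. Changes are in SD units, with positive meaning improvement.

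**Formula.** If the k lowest of 30 on the marker have no Post value, the expected shift is r × S(k) / (30 − k), where S(k) is the sum of the k largest expected normal order statistics in absolute value.
- k = 1: S = 2.043, so the shift is r × 2.043 / 29 = 0.0704r.
- k = 3: S = 2.043 + 1.616 + 1.365 = 5.023 (before rounding), so the shift is r × 5.023 / 27 = 0.186r.

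The 95% CI half-width is t(0.975, 29 − k) / √(30 − k): 0.38 SD with 29 pairs and 0.40 SD with 27. The last column is simulated with a true change of zero; its nominal value is 2.5%.

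| Lost | r | Shift (SD) | Share of half-width | Chance of a significant false improvement |
|---|---|---|---|---|
| 1 of 30 | 0.3 | 0.02 | 6% | 3.3% |
| 1 of 30 | 0.5 | 0.04 | 9% | 3.9% |
| 1 of 30 | 0.8 | 0.06 | 15% | 5.4% |
| 3 of 30 | 0.3 | 0.06 | 14% | 4.9% |
| 3 of 30 | 0.5 | 0.09 | 24% | 7.4% |
| 3 of 30 | 0.8 | 0.15 | 38% | 14.1% |

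At r = 0 the shift is zero. If the teens withdrawn are a random draw from the worst 10 on the marker, rather than the very worst, the shifts at r = 0.3 / 0.5 / 0.8 fall to 0.01 / 0.02 / 0.03 SD for one teen and 0.04 / 0.06 / 0.09 SD for three.

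**At the planned effect.** Against d = 0.64, losing one teen adds 0.02 / 0.64 = 3% to 0.06 / 0.64 = 9%. The standardised effect moves slightly more than the mean, because trimming also shrinks the SD. At r = 0.5 the average observed d goes from 0.66 to 0.71 (one teen) or 0.78 (three).

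**What the exploratory models recover.** An all-available-data model was approximated by regressing Post on Month 2 in those remaining and evaluating at the Month-2 mean of all 30, with three withdrawn. Here r is also the correlation between Month 2 and Post.
- Withdrawal follows the recorded Month-2 score of the same scale: remaining shift 0.00 at every r. CRIES and EDE-Q are fully corrected.
- Withdrawal follows a marker that the model does not contain: correction is partial, and depends on how strongly that marker correlates with Month 2. At r = 0.8 the remaining shift is about 0.02 SD when that correlation is 0.9, and about 0.11 SD when it is 0.3.
- SF12 has no interim value, so its model has nothing to correct from. The shift stays at 0.06 / 0.09 / 0.15 SD for r = 0.3 / 0.5 / 0.8.

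**The case against.** The strongest reply is that several things must all happen: a teen deteriorates significantly, staff choose withdrawal over support, Post is not obtained, and the outcome tracks the deterioration. The text establishes only that the second is allowed. Withdrawal is discretionary, other sections describe support alone, and nothing forbids a Post battery for a withdrawn teen. The sentence sits in a risk section rather than a data-collection section, and the consent pages, which might address data after withdrawal, are not in the public document. All of this stands, and it is why the point is conditional and minor.

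A second reply is that the real gap is the lack of any rule for a missing Post value in the t-tests. That would affect all dropout, which the plan puts at 20%, or 6 of 30. This is fair. Withdrawal for deterioration still deserves separate mention, because it is selected on worsening and is the study team's own decision.

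A third is that the plan already has safeguards. The models help CRIES and EDE-Q, and since mood, eating and trauma scales are recorded at Months 1 and 2, a wholly unrecorded trigger is the less likely case for EDE-Q. The models do not help the t-tests or SF12. The attendance check may reveal the pattern but recovers no value. The attrition alerts begin at 35%, or 11 of 30 teens, so a few withdrawals would not trigger them.

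A reader might infer that the plan hides harm. It does not: retention and adverse events are reviewed separately under item 12 and would still show the withdrawal. A reader might also infer that deteriorating teens must leave, or that their Post data are barred. The wording supports neither.

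**Conclusion.** The point holds as a minor design matter. The plan permits exit from the study on deterioration and states no intention to obtain Post afterwards. If Post is then missing, the paired t-tests cannot use that teen, and the estimated change leans toward improvement.

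With the number withdrawn and the correlation both assumed, the lean is about 0.02 to 0.06 SD for one teen of 30, well inside a half-width of 0.38 SD. The 0.06 to 0.15 SD for three teens is a high-end case, and the 14.1% false-improvement figure needs three withdrawals, correlation 0.8 and no true effect all at once. There is no shift if nobody is withdrawn, if Post is obtained, or if the outcome is unrelated to the deterioration.

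For CRIES and EDE-Q the exploratory models correct the shift fully or partly, depending on what drives withdrawal; for SF12 they cannot. It would go too far to conclude that the pilot's efficacy result is unreliable on this account. The documents do not show that any such withdrawal will occur.

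**What to change.** - In Section I, item 10, reword so that significant deterioration may lead to stopping study treatment, and add that this does not end study participation. The clinical decision stays with the team.
- State that every enrolled teen, including those off treatment, is invited at 3 months to at least SF12, CRIES and EDE-Q, unless consent or assent is withdrawn or assessment is clinically inappropriate.
- In item 13, report beside the efficacy results how many teens were taken off treatment for deterioration and how many of them gave Post data.

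**Cost.** A protocol amendment, and possibly revised consent and assent wording. The surveys already run on Qualtrics (Section IV, item 2). At the existing Post rate (Section VI, item 2), payment is $40 + $20 = $60 per family, so $60 to $180 for one to three families. Keeping to the three surveys avoids repeating the interviews that form part of the full Post battery. Three months' availability is already an inclusion criterion.

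**Downsides.** Some teens will decline, the Post scores of those off treatment will partly reflect care received after referral, and the estimate may be less favourable.
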